11.2.1 List of Tables

- Response rate table by B cell subset, visit number (visit month), and treatment group.
- Summary statistics (minimum, 25th percentile, median, 75th percentile, maximum, mean, standard deviation) among all participants, by B cell subset, visit number (visit month), and treatment group.
- Summary statistics (minimum, 25th percentile, median, 75th percentile, maximum, mean, standard deviation) among positive responders by B cell subset, visit number (visit month), and treatment group.
- Table of comparison of Env-specific B cells response rates between treatment groups by B cell subset and visit
- Table of comparison of Env-specific B cell response magnitudes between treatment groups by B cell subset and visit among all responders and positive responders only.

11.2.2 List of Graphs

- Boxplots of % HIV-1 Env-specific B cell by protein, visit number (visit month), and treatment group.
- Spaghetti plots of % HIV-1 Env-specific B cell by protein and treatment group.
- Reverse CDFs of % HIV-1 Env-specific B cell by protein, visit number (visit month), and treatment group.
- Scatterplot of % HIV-1 Env-specific B cell at Month 2.5 vs. prime interval, by protein for Part A
- Scatterplot of % HIV-1 Env-specific B cell at Month 6.5 vs. prime interval, by protein for Part A

- Scatterplot of % HIV-1 Env-specific B cell at Month 6.5 vs. boost interval, by protein for Part A

11.3 Neutralizing Antibody (NAb)

Neutralizing antibodies (NAb) against the autologous strain as well as heterologous tier 1A and tier 2 strains of HIV-1 will be measured in TZM-bl cells as a function of reduction in Tat-induced luciferase (Luc) reporter gene expression after a single round of infection with molecularly cloned, Env-pseudotyped viruses. TZM-bl (also called JC57BL-13) is a HeLa cell clone that was engineered to express CD4 and CCR5 and to contain integrated reported genes for firefly luciferase and *E. coli* β -galactosidase under control of an HIV-1 long terminal repeat (LTR). The cells are highly permissive to infection by most strains of HIV, including primary HIV-1 isolates and molecularly cloned Env-pseudotyped viruses. DEAE-dextran is used in the medium during neutralization assays to enhance infectivity. Expression of the reporter genes is induced in trans by viral Tat protein soon after infection. Luciferase activity is quantified by luminescence and is directly proportional to the number of infectious virus particles present in the initial inoculum. The assay is performed in 96-well culture plates for high throughput capacity. Use of a clonal cell population provides enhanced precision and uniformity. The assay has been formally optimized and validated for single-round infection with either uncloned or molecularly cloned Env-pseudotyped viruses produced by transfection in 293T cells.

Assays will be performed using cryopreserved serum samples starting at a 1:10 dilution. Titers will be defined as the serum dilution that reduces relative luminescence units (RLU) by 50% and 80% relative to the RLU in the virus control wells after subtraction of background RLU in control wells (ID50 and ID80). Neutralization ID50 and ID80 titers will be measured against BG505/T332N (autologous strain) and MW965.26 (heterologous tier 1A strain). Any samples that are positive (ID50>10) against BG505/T332N will be assayed against the 9 virus global panel of heterologous tier 2 viruses: 246F3, Ce1176, CNE55, X1632, Ce0217, BJOX2000, 25710, TRO11, and CH119.

A response is considered positive if the neutralization titer is above 10, the starting dilution, which is the limit of detection of the assay. Magnitude of response will be measured by the natural log of the ID50 and ID80 titer. An aggregate measure of response will be calculated as the area-under-the-magnitude-breadth curve (AUC-MB), which is equivalent to the mean log titer across all viruses in tier 2. If a titer is left censored, half the left censor limit will be used as the titer value.

For Part A of the study, neutralization titers will be measured on samples from the primary immunogenicity time point, week 10 (visit 9 – 2 weeks post 2nd vaccination) and as applicable, week 26 (visit 13 – 2 weeks post optional 2nd boost). Specimens from other time points may also be analyzed at the discretion of the PI, which may be contingent on the results of the primary immunogenicity time point. Those time points may include week 0 (visit 2 – baseline), week 2 (visit 6 – 2 weeks post 1st vaccination), and/or week 32 (visit 14 – 6 months post 2nd vaccination). For those who consented to the optional second boost, additional time points may include week 0 (visit 2 – baseline), week 2 (visit 6 – 2 weeks post 1st vaccination, week 24 (visit 11 – optional 2nd boost visit), week 52 (visit 15 – 6 months post optional 2nd vaccination), and/or week 78 (visit 16, 12 months post optional 2nd vaccination). Data from the two placebo groups in Part A (P1 and P2) will be pooled as Group C1.

For Part B of the study, neutralization titers will be measured on samples from the primary immunogenicity time point, week 10 (visit 9 – 2 weeks post 2nd vaccination) and week 26 (visit 13 – 2 weeks post 3rd vaccination). Specimens from other time points may also be analyzed at the discretion of the PI, which may be contingent on the results of the primary immunogenicity time point. Those time points may include week 0 (visit 2 – baseline), week 52 (visit 15 – 6 months post 3rd vaccination), and/or week 78 (visit 16, 12 months post optional 2nd vaccination). Data from the four placebo groups in Part B (P3, P4, P5, and P6) will be pooled as Group C2.

11.3.1 List of Tables

- Response rate table by cell type, isolate, visit number (visit month), and treatment group.
- Summary statistics for NAb titers (minimum, 25th percentile, median, 75th percentile, maximum, mean, standard deviation) among all participants, by cell type, isolate, visit number (visit month), and treatment group.
- Summary statistics for NAb titers (minimum, 25th percentile, median, 75th percentile, maximum, mean, standard deviation) among positive responders by cell type, isolate, visit number (visit month), and treatment group.
- Listing of neutralizing antibody titers among positive responders.

11.3.2 List of Graphs

- Boxplots of neutralizing antibody titers by cell type, isolate, visit, and treatment group.
- Spaghetti plots of neutralizing antibody titers over time by cell type, isolate, and treatment group.
- Reverse CDFs of neutralizing antibody titers by cell type, isolate, visit and treatment group.
- Scatterplot of neutralizing antibody titers at Month 2.5 vs. prime interval, by cell type, isolate for Part A
- Scatterplot of neutralizing antibody titers at Month 6.5 vs. prime interval, by cell type, isolate for Part A
- Scatterplot of neutralizing antibody titers at Month 6.5 vs. boost interval, by cell type, isolate for Part A

11.4 Binding Antibody Multiplex Assay (BAMA)

Serum HIV-1-specific total binding IgG antibody responses will be measured at the 1:50 dilution against the gp41 and BG505 SOSIP.664 AviB antigens on samples collected from Part A and Part B's participants at week 0 (visit 2 – baseline), week 10 (visit 9 – 2 weeks post 2nd vaccination), and if applicable, week 26 (visit 13 – 2 weeks post optional 2nd boost or 3rd vaccination), week 32 (visit 14), week 52 (visit 15), and week 78 (visit 16). Data from the placebo groups in Part A (P1 and P2) and Part B (P3, P4, P5, P6) will be pooled as Group C1 and Group C2 respectively.

BAMA testing for Part C will include the Trimer 4571 antigen and will be performed on all available participant serum samples collected from Part C study arm groups 7 and 8 at visits 2 (month 0, baseline), 9 (month 2.5, 2 weeks post second vaccination), 13 (month 6.5, 2 weeks post third vaccination), 15 (month 12, 6 months post third vaccination), and 16 (month 18, 12 months post third vaccination).

The assay readout is from a Bio-Plex instrument (Bio-Rad). The Bioplex software provides 2 readouts: a background-subtracted mean fluorescent intensity (MFI), where background refers to a plate level control (i.e., a blank well run on each plate), and a concentration based on a standard curve. Net MFI (MFI*) is MFI minus Neg, where 'Neg' refers to a sample-specific background measure. Samples from post-enrollment visits are declared to have positive responses if they meet three conditions: (1) the MFI* values are greater than or equal to the antigen-specific cutoff (based on the 95th percentile of the baseline visit serum samples and at least 100 MFI), (2) the MFI* values are greater than 3 times the baseline (day 0) MFI* values, and (3) the MFI values

are greater than 3 times the baseline MFI values. Net MFI is used to summarize the magnitude at a given time-point. If sufficient immunogenicity is observed, samples may be titrated to calculate antibody titers (AUC), in which case geometric mean titers between treatment groups at each time point will be compared using two-sample T-test comparing the means of log AUC.

In addition, HIV-1-specific total binding IgA antibodies, binding to IgG subclasses (IgG1, IgG2, IgG3, and IgG4), and Fc-mediated antibody functions (e.g. fragment crystallizable receptor (FcR) array) may also be assessed. Specimens from other timepoints may also be assayed based on results of the initial assay. Other exploratory analyses will examine HIV-1 Env IgG and IgA antibody titers in mucosal (rectal and vaginal) tissues and secretions. Mucosal binding antibody magnitude is quantified in terms of specific activity (SA). SA is defined as $\text{MAX}(0.0002, \text{MFI-Blank}^* \text{dilution} / \text{total antibody concentration})$.

Several criteria are used to determine if data from an assay are acceptable and can be statistically analyzed. The blood draw date must be within the allowable visit window as determined by the protocol. Second, if the blank bead negative control exceeds 5,000 MFI, the sample will be repeated. If the repeat value exceeds 5,000 MFI, the sample will be excluded from analysis due to high background.

11.4.1 List of Tables

- Response rate table by isotype, antigen, visit number (visit month), and treatment group.
- Summary statistics of MFI* values (minimum, 25th percentile, median, 75th percentile, maximum, mean, standard deviation) among all participants, by isotype, antigen, visit number (visit month), and treatment group.
- Summary statistics of MFI* values (minimum, 25th percentile, median, 75th percentile, maximum, mean, standard deviation) among positive responders by isotype, antigen, visit number (visit month), and treatment group. (Mucosal specimens only)
- Summary statistics of specific activity (minimum, 25th percentile, median, 75th percentile, maximum, mean, standard deviation) among all participants, by isotype, antigen, visit number (visit month), and treatment group. (Mucosal specimens only)
- Summary statistics of specific activity (minimum, 25th percentile, median, 75th percentile, maximum, mean, standard deviation) among positive responders by isotype, antigen, visit number (visit month), and treatment group. (Mucosal specimens only)
- Summary statistics of binding antibody titers (AUC) (minimum, 25th percentile, median, 75th percentile, maximum, mean, standard deviation) among all participants, by isotype, antigen, visit number (visit month), and treatment group. The 95% CI will be calculated based on a normal approximation for log-transformed AUC.
- Summary statistics of binding antibody titers (AUC) (25th percentile, median, 75th percentile, maximum, mean, standard deviation) among positive responders, by isotype, antigen, visit number (visit month), and treatment group. The 95% CI will be calculated based on a normal approximation for log-transformed AUC.
- Tables of comparison of geometric means of binding antibody titers (AUC) between treatment groups by isotype, antigen, and visit among all participants and among positive responders.

11.4.2 List of Graphs

- Boxplots of MFI* values by isotype, antigen, visit, and treatment group.
- Boxplots of binding antibody titers (AUC) by isotype, antigen, visit, and treatment group.
- Boxplots of specific activity by isotype, antigen, visit, and treatment group. (Mucosal specimens only)
- Magnitude-Breadth curves grouped by individual treatment arms and pooled treatment arms
- Scatterplot of binding antibody titers at Month 2.5 vs. prime interval, by isotype, antigen for Part A
- Scatterplot of binding antibody titers at Month 6.5 vs. prime interval, by isotype, antigen for Part A
- Scatterplot of binding antibody titers at Month 6.5 vs. boost interval, by isotype, antigen for Part A

11.5 Trucount Assay

The Trucount® pan-lineage panel is designed to provide counts for the major lineages found among leukocytes in blood. It is used on whole blood with Trucount® beads to allow for determination of absolute cell concentrations. There is a fixed number of beads within each sample at the time of staining and the number is determined by the Trucount® lot number. Whole blood stained for Trucount® is analyzed on an LSR II cytometer. Unlike a functional assay, there are no functional negative or positive controls.

The primary Trucount readout endpoints are cell subset concentrations (cells/ μ l blood) and cell subset percentages. Subset concentrations and cell percentages of interest include total PBMCs, neutrophils, CD11b+ neutrophils, CD16+ neutrophils, total monocytes, CD86+ monocytes, classical monocytes, CD86+ classical monocytes, non-classical monocytes, CD86+ non-classical monocytes, intermediate monocytes, CD86+ intermediate monocytes, lymphocytes, CD3+ T cells, CD4+ T cells and their activated (CD38+, CD38+DR+ double positive, CD69+, HLA-DR+) subsets, CD4- CD8- T cells and their activated (CD38+, CD38+DR+ double positive, CD69+, HLA-DR+) subsets, CD8+ T cells and their activated (CD38+, CD38+DR+ double positive, CD69+, HLA-DR+) subsets, total NK cells, 16+56+ NK cells, 16+56- NK cells, 16-56- NK cells, dendritic cells and their CD86+ subset, myeloid dendritic cells (mDC), CD86+ mDCs, plasmacytoid DC (pDC), CD86+ pDC, CD19+ B cells, and CD20loCD38hi plasmablasts CD19+ B cells and their CD86+ subset. Cell concentrations are calculated based on the relative proportion of Trucount® beads in each tube, and percentages are calculated based on parent populations. Concentrations are calculated taking into account the dilution factor introduced by the ACD liquid anticoagulant.

Trucount® assays are planned for up to 88 participants from Part B and 22 participants from Part C. Assay data over time at innate immune time points, Day 0, 1, 3, 7, 56 and 168 are available after the first vaccination. The blood samples at innate immune time point, Day 0, were collected prior to the vaccination. The cell concentrations at Day 0, therefore, will be treated as baseline measures for the cell concentrations at the later innate immune time points (Days 1, 3, 7, 56, 168) after the same vaccination.

The cell concentrations will be presented on the log-scale graphically and be log-transformed prior to statistical analysis. Cell percentages will be presented and analyzed on the linear scale.

The following comparisons of innate immune responses over time within each Group or between Groups within a time point will be done:

- The innate immune responses at Days 1, 3, 7, 56, and 168 will be compared to the innate immune responses at Day 0 within each group. The comparisons will be done using a linear mixed effect (LME) model with random effect for subject and fixed effects for Group and Day (modeled as a factor variable), with an interaction between Day and Group. Both log-cell concentrations and cell percentages will be evaluated—in separate mixed effects models. The assumptions of the LME will be evaluated using standard diagnostics, e.g. by plotting residuals.

11.5.1 List of Tables

- Summary statistics (i.e., min, mean, median, max) of the cell concentrations by innate immune time points (Days 0, 1, 3, 7, 56, 168) and treatment group
- Summary statistics (i.e., min, mean, median, max) of the cell percentages by innate immune time points (Days 0, 1, 3, 7, 56, 168) and treatment group

11.5.2 List of Graphs

- Plots of individuals' cell concentrations over time by treatment with the median for each treatment group superimposed on the individuals' profiles. The cell concentrations will be plotted on the log scale.
- Plots of individuals' cell percentages over time by treatment group with the median for each treatment group superimposed on the individuals' profiles.

11.6 Electron Microscopy Polyclonal Epitope Mapping (EMPEM)

Polyclonal antibodies (IgG) are isolated from individual (participant) blood samples using commercial Fc-affinity purification resins. The antibodies are enzymatically digested into the fragment antigen binding (Fab) components with papain, and incubated with soluble, HIV Env trimer proteins, matched to the immunogen used in the study (BG505 SOSIP.664 or Trimer 4571). The complex is purified by size-exclusion chromatography, adsorbed onto electron microscopy (EM) grids, stained, and imaged. Individual protein complex particles are extracted from the images and subjected to averaging and classification in 2D and 3D space. 3D focused classification methods are used to evaluate each of the defined epitopes on the surface of Env, both in qualitative and quantitative (the magnitude of the given epitope response) terms. The end results are 3D EM maps that are matched to known structures of Env in complex with antibodies and each polyclonal Fab specificity is assigned a final epitope label based on overlap with known structure(s).

The non-quantitative results are graphical and illustrative representations of all unique Env epitopes detected, as a function of individual and timepoint. The quantitative results are per-epitope EMPEM magnitudes, calculated as a function of the number of particles containing a given polyclonal Fab relative to the total number of particles evaluated in 3D space. The per-epitope magnitude value is on a scale of 0-3 to account for trimeric Env having up to 3 copies of a given epitope. It is analogous to stoichiometry (i.e. a value of 3 suggests that all particles had all three copies of the same epitope fully occupied by polyclonal Fab). Note that protomers are an observed phenotype (trimer dissociation/disassembly) and not a unique antibody. These epitopes

cannot be accurately mapped and as such have only non-quantitative results. Summaries of response are number of epitope-specific antibodies detected, the relative abundance of each epitope-specific antibody in a given sample, and number of epitope-specific antibodies excluding responses detected to the gp41-base. Serum specimens are collected from participants enrolled in Parts A, B, and C at visit 9 (week 10) and visit 13 (week 26). The assay is further described in Bianchi et al. (2018), Turner et al. (2023), and Hahn et al. (2024).

The epitopes assignments are: gp41-base, V1V2V3, gp41-GH, C3V5, CD4bs, gp120-GH, gp120-gp120, and gp41-FP (GH: glycan hole, FP: fusion peptide, CD4bs: CD4 binding site). If antibody-induced trimer disassembly is detected during 2D classification, the sample is also assigned a label: protomers.

Examples of EMPEM-derived 3D maps and the location of each epitope with respect to HIV Env ectodomain are shown in Figure 1.

[figure not shown]

Figure 1 Visualization of EMPEM-derived 3D maps. A) Representative maps of antibody-trimer complexes for all defined EMPEM epitopes. B) Overlay of antibodies to the 8 defined EMPEM epitopes.

11.6.1 List of Tables

- Response rate table by epitope, visit number (visit month), and treatment group.
- Response rate table of antibody-induced trimer disassembly (detected protomers) by visit number (visit month) and treatment group.
- Summary statistics (mean, median) of epitope-specific antibodies (with and without responses directed to the base, excluding protomers) by treatment group and visit number (visit month)

11.6.2 List of Graphs

- Box and bar plots show both response rates and the distribution of magnitude by epitope where the boxplot is drawn around only positive responders

- Box and bar plots show the rate of any positive response across all epitopes, and the distribution of the number of epitope-specific responses, where the boxplot is drawn around those positive for at least one epitope. This is shown with and without counting the gp41 base epitope
- Box and bar plots show the rate of any positive response across all epitopes and the distribution of total magnitude, with or without including the gp41-base, where the boxplot is drawn around only positive responders
- The above box and barplots are repeated, where boxplots show the distribution of response among all participants, not just among positive responders
- Bar plots illustrate the percentage of participants with protomers detected
- A participant-level plot shows which epitopes were positive for each participant and treatment group

11.7 Infected cells antibody binding assay (ICABA)

The ICABA assay is conducted to address the exploratory objective to evaluate immunogenicity of the vaccine regimens for Parts B and C. ICABA will detect the presence of antibodies binding to the surface of HIV-1 infected cells in the serum of participants using Infectious Molecular Clone (IMC)-infected target cells.

For the analysis, ICABA assays will be performed on participants' sera from Parts B and C for v2 (M0) and v13 (M6.5). In the ICABA, eight-six participant samples can be tested per plate. All participant samples from this study can be run in two assays of two plates total (one plate of mock and one plate of infected cells).

CEM.CCR5.NKR cells infected with HIV-1 IMC BG505 and mock-infected cells will be tested in a 96-well plate for the ICABA. Participant sera in addition to controls will be incubated with the IMC-infected cells and the presence of bound antibodies will be detected on the surface of the cells using flow cytometry. If the infected cell mock- and baseline-subtracted %IgG+ at 1:100 dilution is >5%, it is considered positive.

11.7.1 List of Tables

- Response rate table by visit number (visit month) and treatment arm
- Summary statistics (i.e., min, mean, median, max) among all participants by visit and treatment arm
- Summary statistics (i.e., min, mean, median, max) among positive responders by visit and treatment arm

11.7.2 List of Graphs

- Boxplot of mock- and baseline-subtracted %IgG+ by visit and treatment arm.
- Spaghetti plot of mock- and baseline-subtracted %IgG+ over time by treatment arm.

11.8 Antibody-Dependent Cell-mediated Cytotoxicity (ADCC)

The established GranToxiLux (GTL) and Luciferase assays will be used to assess response rates and magnitude of serum ADCC. ADCC assays will be performed on participants' sera from Parts B and C for v2 (M0), v9 (M2.5), and v13 (M6.5).

CEM.CCR5.NKR cells infected with HIV-1 IMC BG505 will be tested in a 96-well plate for the Luciferase ADCC assay. Participant sera in addition to controls will be incubated with the IMC-infected cells, and ADCC will be detected through the use of Vivirene luminescence. To assess breadth, CEM.CCR5.NKR cells infected with HIV-1 CAP8, CH058, SUMA, and WITO, and three additional IMCs (to be determined), individually, will be tested in a 96-well plate for the Luciferase assay.

CEM.CCR5.NKR cells coated with Clade A BG505 gp120 will be tested in a 96-well plate for the GranToxilux (GTL) assay. Participant sera in addition to controls will be incubated with the HIV protein, and ADCC will be detected through the use of granzyme B substrate (GTL).

The following evaluation criteria will be employed for these assays:

- i) Luciferase: The data from the luciferase assay is semiquantitative. The peak of specific killing and area under the curve (AUC) will be compared between the placebo and vaccine groups.
- ii) GTL: The data from the assay is quantitative. The frequency of positive responses (% responders) peak ADCC, and area under the curve (AUC) will be tabulated to assess differences in ADCC response between the treatment groups.

Positivity criteria are as follows:

- i) Luciferase: peak % loss Luciferase activity $\geq 10\%$, after background subtraction of baseline response and positivity at one of the first two dilutions.
- ii) GTL: peak activity $\geq 8\%$

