9.4 Immunogenicity analysis

9.4.1 General approach

For the statistical analysis of immunogenicity endpoints, data from enrolled participants will be used according to the initial randomization assignment regardless of how many injections they received. Additional analyses may be performed, limited to participants who received all scheduled injections per protocol. Assay results that are unreliable, from specimens collected outside of the visit window, or from HIV-infected participants postinfection are excluded. Since the exact date of HIV infection is unknown, any assay data from blood draws 4 weeks prior to an infected participant's last seronegative sample and thereafter may be excluded. If an HIV-infected participant does not have a seronegative sample postenrollment, then all data from that participant may be excluded from the analysis.

Data from placebo arms will be pooled across groups ($n = 8$ for analysis in Part B). For analyses of immunogenicity after the second vaccination, data on the 3M-052-AF from Part A (with the maximum tolerated dose of the 3M-052-AF) and Part B will be pooled. Otherwise, analyses of immunogenicity will be performed separately for Part A and Part B participants.

Discrete categorical assay endpoints (e.g., response rates) will be analyzed by tabulating the frequency of positive response for each assay by antigen and treatment arm at each timepoint for which an assessment is performed. Crude response rates will be presented with their corresponding 95% confidence interval estimates calculated using the score test method [1]. Because of the small numbers of control participants in each group, no adjustment will be made to the vaccine arm estimates for the false positive rates (FPRs) in the control arms. Barnard's test will be used to compare the response rates of any 2 vaccine arms, with a significant difference declared if the 2-sided p-value is ≤ 0.05 .

For quantitative assay data (e.g., percentage of positive cells from ICS assay), graphical and tabular summaries of the distributions by antigen, treatment arm, and timepoint will be made. For all primary and secondary immunogenicity endpoints, box plots and plots of estimated reverse cumulative distribution curves (CDFs) will be used for graphical display of all of the study arms. Typically, the results will be shown for each vaccine arm and for the pooled placebo group.

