11.8.1 List of Tables

Luciferase:

- Response rate of peak background subtracted percent killing or loss luciferase activity by antigen, visit number (visit month), and treatment arm
- Summary statistics (i.e., min, mean, median, max) of peak background subtracted percent killing or loss luciferase activity among all participants by antigen, visit, and treatment arm
- Summary statistics (i.e., min, mean, median, max) of peak background subtracted percent killing or loss luciferase activity among positive responders by antigen, visit, and treatment arm
- Summary statistics (i.e., min, mean, median, max) of pAUC of background subtracted percent killing among all participants by treatment group, protein, and visit
- Summary statistics (i.e., min, mean, median, max) of pAUC of background subtracted percent killing among positive responders by treatment group, protein, and visit
- Response rate comparison using Barnard's exact test

GTL:

- Response rate of peak activity by antigen, visit number (visit month), and treatment arm
- Summary statistics (i.e., min, mean, median, max) of peak activity among all participants by antigen, visit, and treatment arm

- Summary statistics (i.e., min, mean, median, max) of peak activity among positive responders by antigen, visit, and treatment arm
- Summary statistics (i.e., min, mean, median, max) of AUC by treatment group, protein, and visit
- Summary statistics (i.e., min, mean, median, max) of AUC among positive responders by treatment group, protein, and visit

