11.9 Antibody-Dependent Cellular Phagocytosis (ADCP)

The Antibody Dependent Cellular Phagocytosis (ADCP) is a qualified assay employing flow cytometric-based technology that measures the ability of antibodies to mediate phagocytosis. Biotinylated antigen conjugated to neutravidin beads are incubated with patient serum or plasma, purified IgG, or monoclonal antibodies. A monocyte cell line (THP-1) is added to the immune complexes and spinoculated at 4°C followed by incubation at 37°C. Cells are then analyzed for bead internalization by flow cytometry (bead positive versus bead negative detection).

A phagocytic score is determined based on the ratio of experimental sample to PBS control. Mean phagocytosis score is defined as: (% bead positive for participant x MFI bead positive for participant) / (% bead positive for PBS only control x MFI bead positive for PBS only control).

Positivity calls will be based on two criteria:

- i. ADCP score greater than the 95th percentile average of the visit 2 samples.
- ii. ADCP score greater than three-fold over the ADCP score of the sample-specific baseline.

Participants' serum samples at timepoints visit 2 (week 0), visit 6 (week 2), visit 9 (week 10) and visit 13 (week 26) will be analyzed by ADCP for Part B. Assays will be performed at visit 2 (week 0) and visit 13 (week 26) for Part C.

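### Exploratory GTL ADCC positivity (SAP 11.8) ignores the participant's own v2 result, so unchanged background of 8% or more is called a vaccine response

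*SAP*

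**What the plan says.** SAP Section 11.8 plans two ADCC assays, Luciferase and GranToxiLux (GTL), on Part B and Part C sera from v2 (baseline), v9 and v13. It sets a responder rule for each.

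- Luciferase: a peak loss of luciferase activity of at least 10%, "after background subtraction of baseline response and positivity at one of the first two dilutions".
- GTL: "ii) GTL: peak activity" of at least 8%. The rule has no baseline term and no dilution condition.

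Section 11.8.1 keeps the same split. Its Luciferase tables are labelled as background subtracted. The GTL table is "Response rate of peak activity by antigen, visit number (visit month), and treatment arm".

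Section 11.8 gives the GTL responder frequency a purpose: "The frequency of positive responses (% responders) peak ADCC, and area under the curve (AUC) will be tabulated" in order to assess differences between treatment groups. On false positives, Section 9.4.1 says that "no adjustment will be made to the vaccine arm estimates for the false positive rates (FPRs) in the control arms".

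**The concern.** A responder call in a vaccine trial should mark a change that vaccination could have caused. The v2 sera are assayed, so the information to judge change is there, but the GTL call does not use it. Anyone whose GTL peak already reaches 8% before vaccination will count as a responder at v9 or v13 if the reading merely stays where it was.

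Three outputs depend on this flag: the GTL response rate by arm, any comparison of those rates between arms, and the GTL summaries restricted to positive responders (Section 11.8.1). Background positivity would raise the rate in every arm, raise it most in relative terms where the true response is weakest, and pull the arms together. Because Section 9.4.1 rules out correction from the control arms, the individual call is the only safeguard.

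**Working it through.** **1. The responder rules side by side.**

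| Assay (SAP section) | Own pre-vaccination result used in the call? |
|---|---|
| B-cell phenotyping (11.2) | Yes, Fisher's exact test against visit 2 |
| BAMA (11.4) | Yes, more than 3 times baseline |
| ICABA (11.7) | Yes, mock- and baseline-subtracted, above 5% |
| ADCC Luciferase (11.8) | Yes, baseline subtracted, at least 10% |
| ADCP (11.9) | Yes: "ADCP score greater than three-fold over the ADCP score of the sample-specific baseline" |
| ADCC GTL (11.8) | No, peak of at least 8% |
| NAb (11.3) | No, titer above 10, the stated limit of detection |
| ICS (11.1) | No, judged against negative-control wells |

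GTL is not the only assay without a v2 term. For NAb and ICS, however, the SAP states another reference (the detection limit, the control wells). It states none for the GTL 8%.

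**2. Effect on the response rate.** The SAP states no GTL error rate, so there is no figure to reproduce. Let b be the share at or above 8% at v2 who stay there, and r the true vaccine response rate, independent of b. Then:

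reported rate = b + (1 − b)r

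reported difference between two arms = (1 − b)(r₁ − r₂)

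The SAP does not give b; the values below are assumptions.

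| b | r = 0 | r = 10% | r = 20% | r = 50% | Reported difference, true 50% vs 20% |
|---|---|---|---|---|---|
| 5% | 5% | 14.5% | 24% | 52.5% | 28.5 points |
| 10% | 10% | 19% | 28% | 55% | 27 points |
| 20% | 20% | 28% | 36% | 60% | 24 points |

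For example, 0.10 + 0.90 × 0.10 = 0.19.

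**3. Counts at the planned sizes.** Section 8.3 plans on 18 analysable vaccinees per Part B arm; Section 9.4.1 gives 8 pooled Part B placebo recipients. With no true response, the chance of at least one false responder among 18 is 1 − (1 − b)^18: 60%, 85% and 98% for b = 5%, 10% and 20%. The chance that the placebo group shows none is (1 − b)^8: 66%, 43% and 17%. The placebo group is thus a weak guide to b.

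**4. What a baseline condition does, and costs.** This simulation rests wholly on assumptions: six dilutions, person-specific background with mean 3 and SD 3 points at the first dilution, halving at each further dilution, and assay SD 2. The vaccine effect halves in the same way. The adjusted rule tested is a raw peak of at least 8% and also at least 8% after subtracting v2 at the same dilution.

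| True effect at first dilution | Called positive, raw rule | Called positive, raw and v2-subtracted 8% |
|---|---|---|
| none | about 8.5% | about 0.3% |
| 8 points | 80% | 49% |
| 10 points | 92% | 76% |

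If the background is not allowed below zero, the 8-point row becomes 84% and 51%. With background mean 4 and SD 4 and assay SD 3, non-responders called positive fall from 25% to 6%. The baseline condition removes most false calls, but an unchanged 8% cutoff on the difference loses many real responses of 8 to 10 points.

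**The case against.** Much of the case on the other side stands.

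- ADCC is exploratory: Part B exploratory objective 2, and in Part C only under additional assays. No primary or secondary conclusion rests on it.
- The two assays use different target cells and readouts and already have different cutoffs, and no GTL-versus-Luciferase comparison is planned. Unlike rules are not in themselves a contradiction.
- GTL response rates are tabulated by visit, so with v2 assayed, baseline positivity will be visible by arm. The pooled placebo group is typically shown as well. This informs the reader at group level but leaves each participant's flag unchanged.
- Peak and AUC are also summarized in all participants without the flag.
- Background is independent of randomization. It dilutes a true difference between arms but does not create a false one, and at b = 5% the dilution is only 5% of the difference.

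A reader might infer more: that a spike at any dilution is enough, or that non-specific killing is known to inflate GTL rates materially. The SAP supports neither. That any dilution counts is an inference from the word peak and the absence of a dilution condition. The SAP gives no baseline GTL distribution and does not say whether the readout already subtracts an assay background. Such a subtraction would in any case not replace comparison with the participant's own v2 value.

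**Conclusion.** The point holds in a limited form. As written, the GTL rule labels unchanged background at or above 8% as a vaccine response, and nothing later in the SAP corrects the individual call. The consequence is an inflated response rate in every arm and true differences reduced by the factor (1 − b). For an assumed b of 5% to 20%, a true 10% rate would read 14.5% to 28%. This assumes that baseline positivity persists and is independent of vaccine response. The actual b could be close to zero, and then the effect is negligible.

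It would also be too strong to conclude that 8% after v2 subtraction is the correct rule. Under the assumed noise model that rule trades fewer false calls for a marked loss of detection at 8 to 10 points, and the SAP offers no basis for that cutoff. Because the endpoint is exploratory, this is a worthwhile correction and not a threat to the trial's main conclusions.

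**What to change.** In Section 11.8, add a v2-adjusted GTL responder call: raw peak of at least 8% plus a condition on the participant's own v2 result. The assay laboratory should set the cutoff for that condition from the assay's variability, and the SAP should fix it before the call is derived. The 8% cutoff should not be applied unchanged to the v2-subtracted value without that check.

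Report the adjusted call beside the raw 8% call, by visit including v2. Use the adjusted call for between-arm response rates and for the summaries among positive responders in Section 11.8.1. State which dilutions may supply the GTL peak. A check at the first two dilutions, as for Luciferase, can be added as a sensitivity call only.

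The cost is SAP wording and one flag derived from results already planned. Participants without a v2 result cannot be evaluated for the adjusted call, and some sensitivity to small effects is lost.
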